## **7. DESIGN**

This is a multicenter, randomized, double-blind, placebo-controlled, parallel-group, fixed-amount study using 1 amount of Gelesis100.

At the end of this study, an extension study will be proposed to all subjects who have completed 24 weeks of treatment and lost at least 3% of their body weight from baseline in order to assess the effectiveness and safety of Gelesis100 after an additional exposure of 24 weeks on an open-label basis.

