#### **10.1.4 Post-Treatment Follow-up Period**

The duration of the follow-up period is 28 days with a visit window of 3 days for Visit 14 but no visit window for Visit 13 (see Section 12.1).

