### **12.2.13 Visit 13 (First Follow-up Visit; Day 171; 2 days after Visit 12) (Last visit if entering extension study)**

- New informed consent (subjects entering extension study)
- Physical examination
- Weight
- Waist circumference
- Vital signs (supine and standing blood pressure and heart rate)
- Dietary interview (dietary check)
- IWQOL
- Serum pregnancy test (women of childbearing potential only)
- Serum insulin
- HbA1c
- Serum CRP
- Hematology
- Blood chemistry
- Vitamins
- Concomitant medication record
- AEs and SAEs records

---

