### **12.2.14 Visit 14 (Second Follow-up Visit; Day 197 ± 3)**

- Weight
- Waist circumference
- Vital signs (supine and standing blood pressure and heart rate)
- Dietary interview (dietary check)
- Concomitant medication record
- AEs and SAEs records

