### **13.1.3 Adverse Event and Device Deficiency Recording, Assessment, and Reporting Procedure**

All AEs regardless of seriousness or relationship to the investigational medical device including those occurring during the screening period (after the signature of the Informed Consent Form) are to be recorded in the appropriate electronic CRF.

AEs reported by subject will be discussed in details and recorded by the Investigator at each visit. AEs will be collected until 28 days after the last administration of the investigational medical device (i.e., until subject terminates his/her participation in the study).

The Investigator should specify the date of onset, severity, action taken with respect to the investigational medical device, corrective treatment, outcome, and whether or not there is a reasonable possibility that the AE may have been caused by the use of the investigational medical device.

AEs are graded as follows:

- Mild: sign or symptom, usually transient, requiring no special treatment and generally not interfering with usual activities.

---

- Moderate: sign or symptom, which may be ameliorated by simple therapeutic measures, may interfere with usual activity.
- Severe: sign or symptom intense or debilitating and interfering with usual activities without being immediately life-threatening. Recovery is usually aided by therapeutic measures.
- Very severe: sign or symptom life-threatening. Urgent intervention indicated.

The assessment of the relationship of an AE to the use of the medical device is a clinical decision based on all available information at the time of the completion of the electronic CRF:

- Most probably related: follows a reasonable temporal sequence from medical device use, and cannot be reasonably explained by known characteristics of the subject's clinical data.
- Possibly related: follows a reasonable temporal sequence from medical device use, but could have been produced by the subject's clinical state regardless of the medical device.
- Probably not related: temporal association is such that the medical device use is not likely to have had any reasonable association with the observed event.
- Not related: no relationship to the use of the medical device is perceived.

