### **15.8.7 Safety Assessments**

#### **15.8.7.1 Adverse Events**

All AEs will be presented by number of episodes and by number of subjects experiencing the event in each arm with information on time of occurrence and duration.

AEs (including ADEs) will be coded using the latest version of MedDRA. Treatment-emergent AEs (TEAEs) are defined as events with an onset on or after the first randomized treatment. TEAEs will be summarized by treatment arm, System Organ Class, and Preferred Term. The following TEAEs summaries will be provided:

- TEAEs by severity grade
- TEAEs by relationship to study treatment

In addition, separate summaries of SAEs (SADEs) and AEs (ADEs) resulting in discontinuation of study treatment will be presented.

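### The TEAE definition has no cut-off, and completers who enter the extension leave at Day 171 rather than Day 197, so if Gelesis100 works, post-treatment AEs are ascertained in fewer Gelesis100 than placebo completers

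*Combined protocol and SAP*

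**What the plan says.** Section 15.8.7.1 (Adverse Events) states: "Treatment-emergent AEs (TEAEs) are defined as events with an onset on or after the first randomized treatment". It adds: "TEAEs will be summarized by treatment arm, System Organ Class, and Preferred Term". It gives no last day for counting, no adjustment for follow-up time, and no rule for events that begin after a subject enters the extension. Section 15.8 assigns all safety analyses to the safety population, which Section 15.7.1.3 defines as everyone treated after randomisation.

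Four other places decide how long AEs are observed:

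- **Section 13.1.3:** "AEs will be collected until 28 days after the last administration of the investigational medical device". It equates this point with the end of the subject's participation.
- **Section 10.1.4:** "The duration of the follow-up period is 28 days with a visit window of 3 days for Visit 14". Section 12.2.14 places Visit 14 at Day 197.
- **Section 12.2.13 and the Section 2 flow chart:** Visit 13, at Day 171, is labelled "Last visit if entering extension study".
- **Section 7:** "an extension study will be proposed to all subjects who have completed 24 weeks of treatment and lost at least 3% of their body weight". The extension is open-label.

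Subjects who stop early have the Visit 12 and 13 assessments combined, as soon as possible (Section 14.2.2).

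**The concern.** Dosing ends on Day 168. A completer who does not enter the extension has about 28 days of AE collection off treatment; one who enters has about 3. Section 13.1.3 promises 28 days to everyone, and Section 12.2.13 makes that impossible for entrants.

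The gap is not random with respect to treatment. Eligibility requires at least 3% weight loss, which is measured after randomisation and is what the product is meant to produce. If Gelesis100 works, more of its completers qualify, and fewer of them remain under observation after Day 171. TEAE tables that pool the whole period over all treated subjects would then contain fewer late events on Gelesis100 even if the underlying rates were equal.

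At stake is the safety objective in Section 6.2, which asks for safety and tolerability similar to placebo or clinically acceptable. The tables are descriptive, so the risk is a misleading comparison of late events, not a biased test.

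**Working it through.** **1. The plan's own figure.** Section 15.4 gives 161 completers per arm, a difference of 4.5 points, a margin of 3.0, SD 5.0 and one-sided alpha 0.05. SE = 5 × √(2/161) = 0.557. Power = Φ(1.5/0.557 − 1.645) = Φ(1.047) = 85.2%, matching the stated 85%. These inputs are used below.

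**2. Share eligible for the extension.** With a normal approximation, share = Φ((mean loss − 3)/SD). The documents give no expected placebo loss. I assume 4.1%, the FLOW placebo mean at Day 87 (Section 5.2.1.2, Table 7). FLOW lasted 12 weeks with a stricter diet, so this is only a reference value.

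- Design effect (8.6% vs 4.1%, SD 5): Φ(1.12) = 86.9% on Gelesis100; Φ(0.22) = 58.7% on placebo.
- FLOW effect (6.1% vs 4.1%, SDs 5.1 and 4.4): Φ(0.61) = 72.8%; Φ(0.25) = 59.9%.
- No effect (4.1% in both arms, SD 5): 58.7% in both.

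**3. Completers still followed after Day 171.** Number = 161 × (1 − uptake × share eligible). Uptake is not given, so it is varied and assumed equal in both arms. Example: 161 × (1 − 0.869) = 21 and 161 × (1 − 0.587) = 66.

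| Uptake | Design effect, Gelesis100 vs placebo | FLOW effect | No effect |
|---|---|---|---|
| 100% | 21 vs 66 (ratio 0.32) | 44 vs 65 (0.68) | 66 vs 66 |
| 50% | 91 vs 114 (0.80) | 102 vs 113 (0.91) | 114 vs 114 |
| 25% | 126 vs 137 (0.92) | 132 vs 137 (0.96) | 137 vs 137 |

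At the design effect with a placebo mean of 2% or 3% instead, full uptake gives 39 vs 93 or 30 vs 80, and 50% uptake gives 100 vs 127 or 95 vs 121.

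These counts leave out the 69 anticipated dropouts per arm (230 − 161). If every dropout supplied AEs for 28 days after the last dose, the design case at full uptake would be 90 vs 135.

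**4. Effect on overall TEAE incidence.** This is an illustration with a constant hazard equal in both arms. Let I be the incidence by Day 171, reached over 170 days, with 196 days to Day 197. Non-entrants reach 1 − (1 − I)^(196/170). Arm incidence = (entering share) × I + (1 − entering share) × that value. For I = 50%, the non-entrant value is 55.0%. At full uptake Gelesis100 has 0.869 × 50 + 0.131 × 55.0 = 50.7% and placebo has 0.587 × 50 + 0.413 × 55.0 = 52.1%, a gap of 1.4 points.

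| Incidence by Day 171 | Gap at full uptake | Gap at 50% uptake |
|---|---|---|
| 20% | 0.8 points | 0.4 points |
| 50% | 1.4 points | 0.7 points |
| 80% | 1.2 points | 0.6 points |

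Gelesis100 is lower in every case. The illustration covers completers. If the 30% who drop out had equal incidence in both arms, the gap over all treated subjects would be 0.7 times as large.

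**The case against.** The case against giving this much weight is strong in several respects.

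- **AE collection is bounded.** A reader might infer from the definition alone that TEAEs run on indefinitely. Section 13.1.3 stops collection at 28 days after the last dose. What is missing is an analysis cut-off common to all completers.
- **The size rests on unstated figures.** A reader might also infer that far fewer Gelesis100 subjects are observed late. That needs something near full uptake and the design effect. At the FLOW effect with 50% uptake the counts are close.
- **Not everyone else is followed to Day 197.** Early stoppers, 30% by the plan's own estimate, have a limit counted from their own last dose.
- **The consequence is limited.** No between-arm safety test is planned. Section 15.8.7.1 already calls for time of occurrence, so late events can be identified. Section 11 allows 2 days for remaining product to leave the gut, and the anticipated effects in Section 13.1.4 are gastrointestinal, so many product effects should appear before Day 171.
- **A separate SAP is to hold the detailed conventions** (Sections 15 and 15.8), and it is not in the text reviewed.

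The first four points limit the size, and I accept them. The last does not remove the point. Section 15.8.7.1 already states a definition, nothing reviewed narrows it, and an analysis plan cannot supply off-treatment data that the visit schedule does not collect from entrants.

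**Conclusion.** The point holds as a minor one. AE ascertainment after Day 171 depends on a post-randomisation outcome that the product is meant to change, and the 28-day collection rule conflicts with the Day 171 exit of extension entrants. The direction is predictable if Gelesis100 increases the share losing at least 3%: fewer Gelesis100 completers observed late. The ratio of Gelesis100 to placebo completers followed past Day 171 runs from 0.32 to 0.91 across the design and FLOW effects at 50% to 100% uptake, and is 1.00 with no effect. This rests on an assumed 4.1% placebo loss, normality and equal uptake in both arms.

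The documents do not support reading this as a material distortion of the overall safety profile. The affected window is 26 days, and the illustrative shift in overall incidence at the design effect is about 0.4 to 1.4 points. The distortion is concentrated in events with onset after Day 171.

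**What to change.** In Section 15.8.7.1:

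- For the main between-arm TEAE tables, count events with onset from first study product through Visit 13, or through the combined exit visit for early stoppers, in both arms.
- Show later events in a separate table, with the number of subjects still followed in each arm as denominator.
- State that events after extension entry are not assigned to the randomised arm.

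Reconcile Sections 12.2.13, 13.1.3 and 15.8.7.1 so that the collection period stated for extension entrants is one the schedule can deliver. A common 28-day cut-off would not remove the imbalance, because entrants have no comparable off-treatment period.

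The cost is a short addition to the text and one extra table, with no new data. Off-treatment events move out of the main table but all remain listed. Early stoppers' windows would still vary with their exit date.

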#### **15.8.7.2 Physical Examination**

All physical examination clinically significant abnormal findings will be listed.

#### **15.8.7.3 Vital Signs**

All data from the vital signs assessments (blood pressure, heart rate) will be listed. The data will also be summarized and presented by treatment arm and timepoint.

---

#### **15.8.7.4 Laboratory Tests**

All laboratory values and their changes from baseline will be listed. Laboratory measurements will also be summarized as continuous variable and presented by treatment arm and timepoint.

## **16. STUDY COMMITTEES**

### **16.1 Steering Committee**

To ensure the proper scientific completion of the study, a Steering Committee (Research Coordination Committee) will be established. The Committee will have 7 members. The Sponsor and the Principal Investigator will nominate 6 members for this Committee (2 members from the Sponsor, 4 members from the investigational sites). An additional member will be nominated from the Monitoring Team of the CRO.

The Steering Committee should follow the overall progress of the study, ensure smooth communication, seek to solve any unforeseen events affecting the study, and monitor the progress of the results. The Steering Committee will remain blinded throughout the study.

### **16.2 Data Monitoring Committee**

To ensure the proper safety of the study, a Data Monitoring Committee will be established. The Committee will have 3 members (1 Chairman, 1 Clinical Investigator, and 1 Statistician).

The responsibilities of the Data Monitoring Committee will be detailed in a charter.

## **17. ETHICAL CONSIDERATIONS**

### **17.1 Principles**

The study will be conducted in accordance with the principles established by the 18th World Medical Assembly (Helsinki, 1964) and all applicable amendments established by the World Medical Assemblies and the International Conference on Harmonisation (ICH) guidelines for Good Clinical Practices (GCP), and in compliance with European Norm (EN) International Organization for Standardization (ISO) 14155:2011.

### **17.2 Informed Consent**

The Investigator (or a designated representative) should fully inform the subject of all relevant aspects of the study. Prior to the study start, the written Informed Consent Form must be dated and signed by the subject and by the person who conducted the informed consent discussion. The Informed Consent Form will be translated to the state language of the country where the trial will be conducted in accordance with language requirements in US, Canada, and the EEA [status: 1/2007]. The subject will receive the

Property of Gelesis, Srl. – Strictly Confidential

---

original or the copy of the translated, dated, and signed Informed Consent Form. Any new significant findings will be communicated to the subject.

### **17.3 Ethics Committee/Institutional Review Board**

The Investigator must submit this Clinical Investigation Plan (together with the Informed Consent Form, the Investigator's Brochure, the Investigator's curriculum vitae, and any other relevant document) to the appropriate Ethics Committee/Institutional Review Board after the approval by the Sponsor, and is required to forward to the Sponsor a copy of the written and dated favorable opinion signed by the Chairman of the Ethics Committee/Institutional Review Board with information on the composition of the Committee/Board. The investigational product will not be released at the study site and the study will not start until this copy has been received by the Sponsor.

Submission in Europe can be done by the Investigator or the Sponsor (or designee).

Responsibility for coordinating with Ethics Committee/Institutional Review Board is defined in the Investigator/Sponsor (CRO) Contract.

During the course of the study, any amendment to the Clinical Investigation Plan or any update to the Investigator's Brochure will be sent to the Ethics Committee/Institutional Review Board. Any revision to the Clinical Investigation Plan or the Informed Consent Form must be approved by the Ethics Committee/Institutional Review Board prior to implementation, unless there is a safety issue for the study subject.

Any additional requirements imposed by the Regulatory Authorities or the Ethics Committee/Institutional Review Board should be followed.

If requested, a summary of the study outcome will be sent to the Ethics Committee/Institutional Review Board at the end of the trial.

### **17.4 Confidentiality**

All information provided by the Sponsor or produced during the study is confidential. The Investigator and the Sub-Investigators agree to keep this information confidential and not to disclose it to any third party without the prior written approval of the Sponsor. The Ethics Committee/Institutional Review Board members have also the same obligation of confidentiality.

## **18. ADMINISTRATIVE AND REGULATORY PROCEDURES**

### **18.1 Laws**

The study will be conducted in compliance with laws, regulations, and guidelines of the countries where the study is conducted (US, Canada, Europe).

Property of Gelesis, Srl. – Strictly Confidential

---

## **18.2 Clinical Trials Registration**

This trial will be registered in appropriate clinical trial database(s) consistent with federal law and regulation, FDA guidance, and WHO mandate.

## **18.3 Curriculum Vitae**

An updated copy of the curriculum vitae of the Investigator and the Sub-Investigators will be provided to the Sponsor prior to the start of the study.

## **18.4 Record Retention**

The Investigator must maintain confidential all study documentation and prevent accidental or premature destruction of the documents.

The documents should be retained at least 15 years after the completion of the study. If archiving can no longer be ensured by the Investigator, the Sponsor should be informed and a mutually agreed upon alternative should be proposed. The Investigator must notify the Sponsor prior to destroying any document before the 15-year period.

## **18.5 Data Protection**

The Sponsor should treat the subject's personal data and the Investigator's personal data in compliance with all applicable laws and regulations, and take all appropriate measures to protect the data and prevent access to the data by an unauthorized third party.

## **18.6 Insurance**

The Sponsor certifies that it has a liability insurance policy covering the subjects and the liability of the Investigator and Sub-Investigators. The insurance policy is in accordance with local laws and requirements.

The insurance of the Sponsor does not relieve the Investigator and Sub-Investigators of any obligation to maintain their own liability insurance policy as required by applicable law.

## **18.7 Financial Arrangements**

The sponsor is providing financial support and material through contracts with sites participating in the study. Study subjects may be provided reimbursement for reasonable travel expenses and accommodation associated with the completion of study visits, when appropriate under local regulation.

---

## **19. CLINICAL INVESTIGATION PLAN AMENDMENTS**

Any amendment to the Clinical Investigation Plan requires a written favorable opinion from the Ethics Committee/Institutional Review Board prior to its implementation, unless there are overriding safety reasons. In case a change to the Informed Consent Form becomes necessary following the amendment, the Investigator must receive a favorable opinion from the Ethics Committee/Institutional Review Board prior to the implementation of the change.

## **20. CLINICAL INVESTIGATION PLAN DEVIATIONS**

A Clinical Investigation Plan deviation (protocol deviation) is any change or alteration to the procedures stated in the Clinical Investigation Plan, Informed Consent Form, study materials (e.g., questionnaires), or recruitment process originally approved by the Ethics Committee/Institutional Review Board.

Major protocol deviation is any intentional or unintentional change from the approved Clinical Investigation Plan that adversely affects the risk/benefit ratio of the study, the rights, safety, or welfare of the study subjects or others, or the integrity of the study (ability to draw conclusions from the study data), such as any deviation from subject inclusion and exclusion criteria or subject informed consent procedures, study medication dispensing error, etc.

Minor protocol deviation is any deviation that does not have the potential to negatively impact the willingness of the subjects to participate in the study, the safety of the study subjects, or the integrity of study, such as incomplete/inadequate subject testing procedures, non-compliance with medication regimens, visits performed outside of specified visit windows, etc.

The Investigator is not allowed to deviate from the Clinical Investigation Plan except under emergency circumstances to protect rights, safety, and well-being of the study subjects.

All protocol deviations are to be reported to the Sponsor. Major protocol deviations are to be reported according to local regulations.

## **21. STUDY MONITORING**

### **21.1 Responsibilities of the Sponsor**

The Sponsor is responsible to Regulatory Authorities for ensuring the proper conduct of the study (ethical aspects, compliance, integrity and validity of the data recorded). The main duty of the Monitoring Team is to help the Sponsor (and the Investigator) to achieve this objective. A Monitoring Plan will be prepared before the start of the study. During the study, the Monitoring Team will contact the site at regular intervals (by monitoring visits, phone calls, e-mails, letters, or fax) to review the study progress and

Property of Gelesis, Srl. – Strictly Confidential

---

discuss any relevant issue. The Monitoring Team must check the electronic CRF entries against the source documents.

## **21.2 Responsibilities of the Investigator**

The Investigator should accept and sign the Clinical Investigation Plan. The Investigator is responsible to conduct the study in accordance with the Clinical Investigation Plan, the ICH guidelines for GCP, the EN ISO 14155:2011, and the applicable regulatory requirements. The Sub-Investigators appointed to assist the Investigator will be under direct responsibility of the Investigator. The Investigator agrees to provide reliable data as requested by the Clinical Investigation Plan (through electronic CRF and query) in an accurate and legible manner and to ensure direct access to source documents to the Sponsor's representatives.

## **22. PREMATURE DISCONTINUATION OF THE STUDY OR PREMATURE CLOSE-OUT OF A SITE**

### **22.1 Decided by the Sponsor**

The Sponsor may decide to discontinue the study or to close the site for the following reasons:

- the number of subjects who have completed the study is considered sufficient
- the Sponsor has information on the investigational product leading to a doubt about the benefit/risk ratio
- the aim of the study is no longer of interest
- the Investigator has not included sufficient number of subjects in the study after a reasonable period of time mutually agreed upon
- the presence of breach by the Investigator of a fundamental obligation

The Sponsor must notify the Investigator in writing and also inform the Regulatory Authorities and the Ethics Committee/Institutional Review Board.

